5.1.7 Opening of Subsequent Cohorts

The third or sixth patient in each cohort must be observed for 21 days after the first day of panobinostat (14 days after the first dose of ICE) before dosing in the next cohort can begin. If any patient registered within a cohort does not complete at least one cycle of treatment, that patient will be replaced unless discontinuation is for DLT.

Prior to advancing/changing dose levels a cohort summary must be completed and submitted to the clinical research monitor.

Upon review of clinical outcome after enrolling 10 patients in an expansion cohort in schedule A (Table 5.1), thrombocytopenia was considered profound. Therefore, a new schedule B (Table 5.2) with less doses of panobinostat is being investigated in an expansion cohort of phase I to accrue 10 patients.

5.1.8 Dose Limiting Toxicity

The Principal Investigator will document the overall toxicity profile in detail before deciding whether to initiate cohort expansion, or dose escalation. In the event that Grade 3 or 4 adverse events are obviously unrelated to study drug and thus not dose-limiting, the Principal Investigator will determine whether dose escalation or cohort expansion is required.

5.1.9 Non-hematologic Toxicity

For non-hematologic toxicities, DLT will be defined as any CTCAE v4.0 Grade 3 or greater toxicity except for:

- Grade 3 fatigue.
- Grade 3 or 4 nausea and vomiting lasting less than 72 hours after the last dose of chemotherapy.
- Grade 3 non-hematologic laboratory abnormalities that resolve to Grade 1 or baseline (if the patient entered the study with existing toxicity) within 14 days of the first dose of ICE chemotherapy.

5.1.10 Hematologic Toxicity

DLT for hematologic toxicity, using CTCAE v4.0, will be defined as:

- Grade 4 neutropenia lasting greater than 14 days.
- Grade 4 febrile neutropenia.
- Grade 4 platelet count ($<25,000/\text{mm}^3$) at any time, lasting greater than 14 days.

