5.1.6 Dose escalation

Standard doses of ICE chemotherapy will be used and fixed, while panobinostat doses will be escalated (Tables 5, 5.1, and 5.2). Initially, 3 patients will be treated at each dose level and will be monitored for dose limiting toxicities (DLT) for 14 days from the first dose of ICE. If no DLTs are observed in those 3 patients at the end of the observation period, escalation to the next dose level may commence. If a DLT is observed in 1 of the first 3 patients, the cohort will be expanded to a maximum of 6 patients. If 2 or more DLTs are observed in any cohort, no further escalation will take place. The maximum tolerated dose (MTD) will have been exceeded, and the preceding dose level will be recommended for the Phase-II portion of this study. If DLTs are observed in 0 dose level, -1 dose level will be evaluated for DLTs before recommending it as MTD.

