5.1.13 Maximum Tolerated Dose (MTD)

The MTD will be the highest dose at which no more than 1 in 6 of the patients in the cohort experiences one or more DLTs in the first treatment cycle (21 days from the first dose of panobinostat and 14 days from the first dose of ICE).

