The standard “3+3” design will be used for the phase I portion of the trial. Dose limiting toxicity (DLT) is defined as follows: for non-hematologic toxicities, any CTCAE v4.0 Grade 3 or greater toxicity except for grade 3 fatigue, grade 3 or 4 nausea and vomiting lasting less than 72 hours after the last dose of chemotherapy, and grade 3 non-hematologic laboratory abnormalities that resolve to grade 1 or baseline (if the patient entered the study with existing toxicity) within 14 days of the first dose of ICE chemotherapy; for hematologic toxicities using CTCAE v4.0, grade 4 neutropenia lasting greater than 14 days, grade 3 febrile neutropenia requiring antibiotics, grade 4 febrile neutropenia, and Grade 4 platelet count ($<25,000/\text{mm}^3$) at any time and lasting greater than 14 days. Applying the 3+3 design, the first cohort of 3 patients will be treated at dose level 0 and evaluated for DLT at the end of first cycle. The algorithm is as follows: (1) If 0 out of 3 patients experiences dose-limiting toxicity (DLT), the next cohort of 3 patients will be treated at the next higher dose level. (2) If 1 out of 3 patients develop a DLT, an additional 3 patients will be treated at the same dose level. If no more DLTs develop at this dose, i.e. 1 out of a total of 6 patients develops a DLT, the dose escalation continues for the next cohort of 3 patients. (3) At any given dose, if greater than 1 out of 3 patients or 1 out of 6 patients experience DLT, the dose level exceeds the MTD and 3 more patients will be treated at the next lower dose if there are less than 6 patients already treated at that dose. Following the above scheme, MTD is defined as the highest dose level in which 6 patients have been treated with less than 2 instances of DLT. Given 3 predefined dose levels, it is anticipated that up to 12 eligible patients are required for the dose-finding portion of this trial.

To better estimate the DLT rate, an expansion cohort of 10 patients will be treated at the MTD. If at any time the DLT rate exceeds 33%, then the MTD is too toxic and a lower dose than MTD will be selected for the phase II.

With the addition of Dosing Schedule B, an additional 10 patients will be treated at the MTD in a 2nd expansion cohort but at a different dosing schedule to better evaluate safety and administration of ICE.

Phase II:

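### Grade 4 neutropenia and platelets become DLTs only after more than 14 days, but DLT counting closes 14 days after first ICE and no rule settles episodes still open then

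*Combined protocol and SAP*

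**What the plan says.** Section 5.1.10 lists "Grade 4 neutropenia lasting greater than 14 days" as a DLT. For platelets below 25,000/mm³ the criterion is a grade 4 count "at any time, lasting greater than 14 days". The phase I part of section 10.0 repeats both duration conditions. Its neutrophil items read "grade 4 neutropenia lasting greater than 14 days, grade 3 febrile neutropenia requiring antibiotics, grade 4 febrile neutropenia", so febrile neutropenia carries no duration condition.

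The counting window appears in four places:

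- Section 5.1.6: patients "will be monitored for dose limiting toxicities (DLT) for 14 days from the first dose of ICE".
- Section 5.1.7: the third or sixth patient of a cohort "must be observed for 21 days after the first day of panobinostat (14 days after the first dose of ICE") before the next cohort is dosed.
- Section 5.1.13: the MTD rests on DLTs "in the first treatment cycle (21 days from the first dose of panobinostat and 14 days from the first dose of ICE").
- Section 10.0: the first cohort is "evaluated for DLT at the end of first cycle". Section 5.1.3 sets the ICE cycle at 14 days.

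Section 5.1.8 has the principal investigator "document the overall toxicity profile in detail before deciding whether to initiate cohort expansion, or dose escalation". It does not say how an episode still open at the end of the window is classified.

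**The concern.** The duration that makes a grade 4 cytopenia dose-limiting is longer than the period in which DLTs are counted after ICE starts. Two of the haematologic criteria therefore cannot operate, as written, on cytopenia that develops after the combination is given, although the MTD of that combination is the phase I primary objective. Low platelets are also the toxicity that has driven this trial: section 2.5 gives thrombocytopenia as the main reason that ICE was a week late in all 21 patients treated.

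Two decisions are still ahead: the evaluation of the second expansion cohort (10 patients, Schedule B) and the phase II dose, which section 10.0 fixes after expansion. Two careful readers could classify the same open episode differently at either point.

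**Working it through.** **Window.** Panobinostat starts on day -6 and ICE on day 1 (section 5.1.5, Table 5.1). Days -6 to 14 inclusive are 21 days and days 1 to 14 are 14 days. This reproduces the 21-day and 14-day figures of section 5.1.13.

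**When an episode qualifies.** More than 14 days can mean at least 15 calendar days, first reached on onset day + 14, or at least 15 elapsed days, reached on onset day + 15.

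| Onset (ICE day) | Calendar count | Elapsed count |
|---|---|---|
| 2 | day 16 | day 17 |
| 5 | day 19 | day 20 |
| 8 | day 22 | day 23 |
| 14 | day 28 | day 29 |

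**Latest onset that can still qualify** = closing day - 14 (calendar) or closing day - 15 (elapsed):

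- closing on day 14: onset by day 0 or day -1;
- closing on day 15: onset by day 1 or day 0.

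Under every convention, onset on ICE day 2 or later fails. Only an episode that begins in the panobinostat lead-in, or at the latest on ICE day 1, can be counted.

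**Two more lenient readings.**

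1. Stretch the first cycle to the three-week cycle mentioned in section 5.1.11. Closing on day 21 gives onset by day 7 or 6, and closing on day 22 gives day 8 or 7. Later onset still fails, and section 5.1.13 fixes 14 days from ICE in any case.
2. Let the window govern onset only. The event then counts, but the stated wait in section 5.1.7 still ends on day 14, before the classification is known.

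**Bound for the 21 patients already treated.** Cycle 2 was due on day 15 and came a week late, on about day 22. Assume that the recovery limits in section 5.2.7, written for phase II, also applied in phase I. The last grade 4 day was then at most 21, so a qualifying episode began by 21 - 14 = day 7 (calendar) or 21 - 15 = day 6 (elapsed). With the 2-day window, ICE on day 24 and a last grade 4 day of 23 give day 9 or 8. In these patients the gap concerns only onset from ICE day 2 to about day 6-9.

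**Is the follow-up long enough to classify?** Under Schedule B the last cycle 1 panobinostat dose is on day 5. Thirty days of adverse event follow-up (section 9.2) then reach day 35, even if nothing more is given. The longest ICE delay before withdrawal ends on day 15 + 14 = 29. Both reach the latest classification day of 28 or 29.

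The documents give no rate for such episodes, so no probability of a wrong dose decision is calculated.

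**The case against.** The strongest reply is that little still depends on the day-14 limit:

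- Sections 5.1.6, 5.1.7 and 5.1.13 govern escalation, which is over, and the Schedule A expansion is complete.
- The 33% check in section 10.0 has no stated window, and it is not restated for Schedule B.
- Open toxicity is not lost from view. Section 6.2 keeps related grade 3 or greater toxicity under follow-up until it resolves, and section 12 follows serious events to recovery.
- Section 5.1.7 shows that thrombocytopenia outside the formal count already led to the lighter Schedule B.
- The onset reading has textual support. Section 5.1.9 ties resolution of laboratory abnormalities to 14 days after first ICE, whereas section 5.1.10 does not. The wait in section 5.1.7 is a minimum keyed to the last patient, so patients treated earlier in a cohort may have been observed for longer.

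Most of this stands, and it limits the reach of the point. It does not supply the missing rule. The follow-up provisions observe the episode without feeding the DLT count. The onset reading is plausible but nowhere stated, and it leaves the wait too short. In phase II, Table 7-1 reduces panobinostat for grade 4 counts of any duration, and toxicity is reviewed after every 10 patients on the panobinostat arm. Both act after the starting dose has been chosen.

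A reader might go further and infer that DLTs were missed, that the declared MTD is wrong, or that severe cytopenia goes unrecorded. The documents support none of these. They report no uncounted episode, one-week delays suggest that very long episodes may be uncommon, and the blood counts are collected.

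**Conclusion.** The point holds as a gap in the counting rule and is worth fixing before the Schedule B evaluation and the phase II dose decision. Applied literally, no grade 4 neutropenia or grade 4 platelet episode starting on ICE day 2 or later can become a DLT on duration. This rests only on the stated durations and day numbering, and holds under either day-counting convention and with closing on day 14 or 15. Febrile neutropenia is unaffected, and lead-in onset can still qualify, so the criteria are not wholly inoperative.

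The remaining effect is limited to how open episodes in the 10 Schedule B patients are classified and to the phase II dose that follows. For the 33% check, the change only makes the counting explicit. The narrower bound for the 21 treated patients depends on the assumption about recovery limits stated in the working.

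**What to change.** Amend sections 5.1.6, 5.1.7, 5.1.13 and 10.0 to say:

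- The 14-day and 21-day window governs the onset of a DLT.
- A grade 4 neutropenia or grade 4 platelet episode still open at ICE day 14 is pending until it resolves or exceeds 14 days, at most about ICE day 28-29. If it exceeds 14 days it is a cycle 1 DLT.
- The Schedule B and phase II dose decisions wait for pending classifications.

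The cost is amendment wording in four places and a wait of up to about two weeks, only when a patient is still at grade 4 on ICE day 14. Weekly blood counts (section 6.2) and existing adverse event follow-up supply the data.

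Three additions are optional: one day-counting convention, a confirming blood count at about episode day 15, and a look back at the counts of the 21 treated patients under the clarified rule.

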5.1.11 Dose Elimination/Holding/Reduction

A scheduled dose of panobinostat may be held no more than 3 consecutive doses in a 2 week cycle of ICE and no more than 6 consecutive doses in a 3 week cycle of ICE. If it is held longer than this specified time, that patient will be removed from study.

For example, if a patient is delayed 1 week to receive a cycle of ICE then 6 consecutive doses of panobinostat may be missed but if ICE is administered every 2 weeks on schedule then no more than 3 consecutive doses of panobinostat may be missed.

For those patients entered in the expanded cohort (Dosing Schedule B) of adjusted panobinostat dosing, panobinostat will be self administered by patient 3x/week starting D-6 and will continue through D5 and be held until start of next cycle of ICE. If ICE is held due to AE and given every 3 weeks, a patient cannot miss more than 6 consecutive doses of panobinostat or will be removed from study.

5.1.13 Maximum Tolerated Dose (MTD)

The MTD will be the highest dose at which no more than 1 in 6 of the patients in the cohort experiences one or more DLTs in the first treatment cycle (21 days from the first dose of panobinostat and 14 days from the first dose of ICE).

5.2 Phase-II

- 5.2.1 The starting dose of panobinostat will be based on the data generated from the phase-I portion of this study.
- 5.2.2 Patients will be randomized by MDACC to arm 1 (ICE) or arm 2 (Panobinostat + ICE) as shown in Table 5.2.
- 5.2.3 For cycle 1 of the panobinostat arm, panobinostat will be given on day -6. (See Fig1)
- 5.2.4 Cycle 3 of both arms will be ICE alone (to minimize any potential effect on stem cell collection)

Table 5.1
Schedule A

Day of cycle	HDACi	Chemotherapy(ICE)			Growth factor
-6	Panobinostat				
-5					
-4	Panobinostat				
-3					
-2	Panobinostat				
-1					
0					
1	Panobinostat	Ifex/Mesna	Carboplatin	Etoposide	
2				Etoposide	
3	Panobinostat			Etoposide	
4					start growth factor support
5	Panobinostat				
6					
7					
8	Panobinostat				
9					
10	Panobinostat				
11					
12	Panobinostat				
13					
14					

Table 5.1.1 Dosing Schedule B

Day of cycle	HDACi	Chemotherapy(ICE)			Growth factor
-6	Panobinostat				
-5					
-4	Panobinostat				
-3					
-2	Panobinostat				
-1					
0					
1	Panobinostat	Ifex/Mesna	Carboplatin	Etoposide	
2				Etoposide	
3	Panobinostat			Etoposide	
4					start growth factor support
5	Panobinostat				
6					
7					
8					
9					
10					
11					
12					
13					
14					

5.2.5 The doses of each drug are shown in the following table 5.2.

Table 5.2. Doses of ICE vs panobinostat + ICE				
	Arm 1 (ICE)	Arm 2 (Panobinostat + ICE) Schedule B		
Day	Drug	Drug	Dose	Infusion time
Starting day -6 and given 3 times per week during cycles 1 and 2		PANOBINOSTAT (LBH589)	MTD determined by phase I	Oral
1	Ifosfamide + Mesna	Ifosfamide + Mesna	5 grams/m ² equal dose of each	IV continuous infusion over 24 hours
2	Mesna	Mesna	2 grams/m ²	IV continuous infusion over 12 hours
1	Carboplatin	Carboplatin	standard dose (target AUC=5mg/ml/min)	IV over 1 hr
1, 2, 3	Etoposide	Etoposide	100 mg/m ² /day	IV over 2 hours
4**(12-48 hrs after completion of ICE)	growth factor support	growth factor support	Standard dose	

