5.1.3 Phase-I dose levels

Panobinostat + ICE combination therapy will be administered at the dose level assigned to each cohort, as outlined in Table 5. Each ICE cycle is considered to be 14 days (2 weeks). A tumor response assessment will be done within 7-13 days of completion of 3 cycles of ICE using the Revised Response Criteria for Malignant Lymphoma. Patients with a complete response (CR) or partial response (PR) will be considered for stem cell transplantation, otherwise they will be removed from the study.

Table-5: Study design for the phase-I		
Dose Level	ICE chemotherapy Day 1 and repeat every 14-days	PANOBINOSTAT (mg, orally) 3 times per week
-1	See Table 5.2	10
0	See Table 5.2	20
1	See Table 5.2	30

5.1.4 Panobinostat is given only during cycles 1 and 2 of ICE according to Table 5.1. Cycle 3 of ICE will be given without panobinostat.

5.1.5 Investigational therapy: Panobinostat (LBH589).

Panobinostat will be provided by Novartis. Oral Panobinostat will be supplied as 5-mg or 20-mg hard gelatin capsules.

Medication labels will comply with US legal requirements and be printed in English. They will supply no information about the patient. The storage conditions for study drug will be described on the medication label.

During the study, Panobinostat will be self-administered (by the patients themselves) orally three times per week.

For cycle 1 of ICE: Panobinostat will be administered starting day -6 and ICE on day 1 as outlined in Table 5.1:

Patients should be instructed to take their oral dose of Panobinostat around the same time each day. Each dose of Panobinostat should be taken with an 8 oz / 240 ml glass of water. Patients should be instructed to swallow the capsules whole and not chew them. Patients must avoid grapefruit or grapefruit juice and seville (sour) oranges during the entire study.

If the patient forgets to take his/her dose on a scheduled treatment day, then he/she should take Panobinostat on that same day within 12 hours after the missed dose if possible. After more than 12 hours, that day's dose should be withheld, and the patient should wait to take Panobinostat until the next scheduled treatment day (i.e., patients should be instructed not to try to make-up the missed dose after 12 hours). The patient should then continue treatment with the original dosing schedule. A pill diary will be provided to the subject for documentation of dosing for each cycle.

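### Table 5.2 labels the phase II panobinostat arm Schedule B, but its dosing row omits B's stop after day 5 and, read literally, gives Schedule A's 15 planned doses instead of 9

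*Combined protocol and SAP*

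**What the plan says.** Section 5.2.2 states: "Patients will be randomized by MDACC to arm 1 (ICE) or arm 2 (Panobinostat + ICE) as shown in Table 5.2". In that table the combination column is headed "Arm 2 (Panobinostat + ICE) Schedule B", and the timing entry for panobinostat is "Starting day -6 and given 3 times per week during cycles 1 and 2". The row names no last day within a cycle.

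Schedule B is set out in two places:

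- The calendar titled "Table 5.1.1 Dosing Schedule B", printed just above Table 5.2, shows panobinostat on days -6, -4, -2, 1, 3 and 5 and nothing later.
- Section 5.1.11 says that dosing three times a week from day -6 "will continue through D5 and be held until start of next cycle of ICE". That sentence is written for the phase I expansion cohort.

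Schedule A (Table 5.1) has the same days plus 8, 10 and 12.

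Two cross-references bear on the point. Section 5.1.7 says that "a new schedule B (Table 5.2) with less doses of panobinostat is being investigated in an expansion cohort of phase I", so it names Table 5.2 as the source for Schedule B. Section 5.1.4 says: "Panobinostat is given only during cycles 1 and 2 of ICE according to Table 5.1", and Table 5.1 is Schedule A. No sentence in the text available to us cites Table 5.1.1.

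**The concern.** The header and the row of one table give different instructions. The missing stop is the only thing that separates Schedule B from Schedule A, so a site that works from the row would give the schedule that the protocol moved away from.

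Section 5.1.7 gives the reason for the move: after the Schedule A expansion cohort, "thrombocytopenia was considered profound". Section 2.5 reports that all 21 patients treated on uninterrupted three-times-weekly dosing had ICE delayed by a week, chiefly for thrombocytopenia.

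The dose-modification rules protect patients only in part. For thrombocytopenia, Table 7-1 holds panobinostat at grade 4 (platelets below 25 x 10^9/L), whereas section 5.2.7 delays ICE until platelets exceed 75,000 per microlitre. A patient between these limits could go on taking the extra doses while ICE waits. Patients take panobinostat themselves (section 5.1.5), so the written schedule has to be unambiguous.

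**Working it through.** The protocol states no total dose count, so there is no figure to reproduce. The check counts dosing days.

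**Inputs**

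- Cycle length: 14 days (section 5.1.3).
- Panobinostat in cycles 1 and 2 only (section 5.1.4; Table 5.2).
- Day -6 lead-in before cycle 1 only (sections 5.1.5 and 5.2.3).
- Schedule A days from Table 5.1; Schedule B days from Table 5.1.1.

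**Planned doses**

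| Reading | Cycle 1 | Cycle 2 | Total |
|---|---|---|---|
| Schedule A | -6, -4, -2, 1, 3, 5, 8, 10, 12 (9) | 1, 3, 5, 8, 10, 12 (6) | 15 |
| Schedule B | -6, -4, -2, 1, 3, 5 (6) | 1, 3, 5 (3) | 9 |
| Table 5.2 row, literal | 3 per week x 3 weeks, day -6 to day 14 (9) | 3 per week x 2 weeks (6) | 15 |

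The literal row equals Schedule A.

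- Excess over B: 15 - 9 = 6 doses, namely days 8, 10 and 12 in each of two cycles.
- Relative excess: 6/9 = 67% above B.
- In milligrams: the phase II dose is not yet fixed. At the phase I levels, 6 x 10 = 60 mg, 6 x 20 = 120 mg and 6 x 30 = 180 mg.

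**Sensitivity**

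- If ICE slips by a week, the literal row adds three doses per delayed cycle: 15 + 3 = 18 with one delayed cycle, 18 + 3 = 21 with two. Schedule B stays at 9.
- If the three lead-in days were repeated before cycle 2, Schedule B would come to 12 doses, because days -6, -4 and -2 of cycle 2 are days 8, 10 and 12 of cycle 1. Section 5.2.3 ties the lead-in to cycle 1, and section 5.1.11 holds the drug until the next ICE cycle begins, so this reading is excluded and 9 is the right count.

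**The case against.** The strongest reply is that the row is shorthand. Section 5.1.11 also describes Schedule B as three times a week from day -6, so that phrase is not peculiar to Schedule A. Section 2.5 identifies the earlier regimen by saying that dosing was continuous, a word the row does not use. Section 5.2.5 presents Table 5.2 as a table of doses, and the Schedule B calendar sits directly above it. Sections 5.1.4 and 5.1.7 are phase I text, and their table numbers may be simple slips. Section 5.2.3 cites a figure that is not in our text and may show the days.

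Much of this stands: a careful reader can recover Schedule B. It does not clear the row. Section 5.1.11 adds the stop that the row lacks, and is confined to the phase I expansion cohort. In phase II the stop therefore rests on a column label and a calendar that no sentence cites. Section 5.2.2 points to Table 5.2 for the arms, and 5.1.7 cites the same table for Schedule B. Even if the figure is correct, the row would still disagree with its own header.

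Two further points are fair. The gap between the two platelet thresholds exists under either schedule. Weekly blood counts (section 6.2), the pill diary and dose recording (section 5.1.5) give some protection. These limit the harm; they do not correct the instruction.

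Section 2.5 leaves the phase II schedule open until the Schedule B cohort has been seen. That is legitimate, but header and row must agree whichever schedule is chosen.

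**Conclusion.** The concern holds. Table 5.2 is internally contradictory: its header means 9 planned doses and its row, read literally, means 15. The count assumes 14-day cycles, a lead-in before cycle 1 only, and no holds, delays or reductions.

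This is an error in a dosing instruction, and it should be corrected before the first phase II randomisation. It is not a missing definition, since Schedule B can be found elsewhere in the protocol. The delay in all 21 patients explains why the extra doses matter, but it does not estimate the risk at the phase II dose, because section 2.5 does not break those patients down by dose level. Nothing is claimed here about the complete response comparison or about patients on mixed schedules.

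**What to change.** - In Table 5.2, replace the panobinostat timing with days -6, -4, -2, 1, 3 and 5 in cycle 1 and days 1, 3 and 5 in cycle 2, and cite Table 5.1.1. If the investigators choose Schedule A instead, change the column header and cite Table 5.1.
- In section 5.1.7, change the Schedule B reference from Table 5.2 to Table 5.1.1.
- In section 5.1.4, cite Table 5.1 for Schedule A and Table 5.1.1 for Schedule B.
- As optional housekeeping before phase II opens, bring the closing sentence of section 2.5 into line with the schedule named in Table 5.2.

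The cost is one table row, two table references and, if wanted, one sentence in an amendment.
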